The outcome parameters used for sample size calculations for objectives 1 and 2 are estimated from the Malezi I program evaluation baseline data (before introduction of CCD program), comparable to what we would expect in the MR intervention group, who have not been exposed to any CCD intervention. From 24-29% of caregivers reported having a local or shop toy in the home, 22% reported singing to the child in the past month, and 7-13% reported reading or writing with the child in the past week.

Objective 1: To determine caregiver radio listenership patterns at baseline, and exposures to the ECD radio messaging nine months' post-intervention, and effect of radio exposure on caregiver ECD perceptions, knowledge and reported parenting practices, using pre-post surveys in a cohort of caregivers of children 0-24 months of age at baseline, in study communities from each intervention arm.

A sample size of 593 enrolled in the MR intervention group will provide 80% to detect a 5% or greater change from baseline (10%) to endline (15%) in the MR intervention group, taking into account 15% LTFU, design effect of 1.2, and estimated correlation of 0.4 between respondents at baseline and endline (Table 3). This sample size will provide even greater power to detect a 10% difference if baseline estimates are higher than 10%.

Table 3. Sample size estimation* parameters, MR group, caregiver cohort, pre-post

Arm	Prevalence of key outcome			Power	Sample size	Adjusted Sample size (15% LTFU, DE 1.2)
	Baseline	Endline	Expected Change			
MR (Malezi radio)	10%	15%	5%	80%	420	593
	20%	30%	10%	99%	419	592
	25%	35%	10%	98%	411	580

*STATA 14 paired proportions large-sample McNemar's test at 5% level significance.

Objective 2: To determine whether the Malezi II full intervention (MRV-CCD) significantly increases caregiver's knowledge and parenting behaviors/practices when compared to radio messaging alone, using a pre-post quasi-experimental evaluation design in a cohort of caregivers of children 0-24 months of age at baseline, in MRV-CCD and MR communities.

The change between baseline and endline in the Malezi I evaluation for the above-mentioned indicators ranged from 10-30% after introduction of the Malezi I CCD program. With the introduction of radio messaging only, we estimate a 5-10% effect size, and about a 20-30% effect size in the full intervention (MRV-CCD) group (Table 4).

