We estimate that a sample size of n=430 caregivers per intervention group will provide 90% power to detect a 15% "difference-in-differences" between the MR and MRV-CCD intervention groups at endline, and >80% power to detect a 5% change in the MR intervention group, and a 20% change in the MRV-CCD intervention group between baseline and endline, at a level of 5% significance. Taking into account a 15% non-retention rate and a design effect of 1.2, we will aim to enroll 1214 into the caregiver cohort or n=607 in each intervention group.

Table 4. Sample size estimation* parameters, MR compared to MRV-CCD groups, caregiver cohort, pre-post and differences-in-differences

Arm	Prevalence of key outcome			Power	Sample size	Adjusted Sample size (15% LTFU, DE 1.2)
	Baseline	Endline	Expected Change			
MR (Malezi radio)	10%	15%	5%	81%	430	607
MRV-CCCD (Malezi radio + radio + CCD program)	25%	45%	20%	>99%	430	607
Difference	15%	30%	15%	90%	860	1214

*Sample Size and Power estimated by a simulation of the DID Analysis using R Software Package.

Objective 3. To determine whether the introduction of short video job aids (training, provision, supportive supervision) to the Malezi II CCD program improves the quality of counseling provided by the CHW in the clinic and the home, using pre-post observation fidelity checklists for all CHWs working in the MRV-CCD communities.

The Malezi I evaluation assessed CHW-reported time spent in the home providing ECD messages to pregnant women or caregivers of children under 5 at baseline (14-17%) and endline (64-74%). While the change was substantial, we estimate that the actual CHW counseling skills would be lower using an observation checklist compared to CHW self-reported behaviors. We conservatively estimate that CHWs in the MRV-CCD intervention group, already trained in the Malezi I CCD program, will score at 50% on the baseline observation checklists in this evaluation, increasing 15-20% after introduction and capacity building in using the short videos.

Table 5 shows that a sample size of 123 CHWs will achieve 80% power to detect a 15% change between baseline and endline in CHW quality of counseling checklist score, taking into account a correlation of 0.4 between measures, a 5% non-retention rate and a design effect of 1.1.

Table 5. Sample size estimation* parameters, MRV-CCD CHW cohort, pre-post

Arm	Prevalence of key outcome			Power	Sample size	Adjusted Sample size (5% LTFU, DE 1.1)
	Baseline	Endline	Expected Change			

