MRV-CCD (Malezi radio + radio + CCD program)	30%	45%	15%	80%	102	118
	50%	65%			106	123
	70%	85%			78	90

*STATA 14 paired proportions large-sample McNemar's test at 5% level significance.

Selection Criteria for Study Communities

The study will be implemented in probability selected geographic areas of the catchment villages surrounding selected health facilities in four districts of Tabora region. The health facilities will be purposefully selected, including the district hospital in each of the four districts. Each primary health facility has clearly designated villages assigned to that facility (about 3-7), and each village has recognized boundaries, administrative units and census enumeration areas (EA), defined by the National Bureau of Statistics (NBS). Further details on sampling EA units are described later in this protocol. District hospitals do not have village catchments because they are secondary level facilities, but up to about 7 villages immediately surrounding the district hospital will be included in the sampling frame.

All facilities will meet the following eligibility criteria at baseline:

1. Accessible by road in all seasons
2. Has at least 3 CHWs and sufficient health provider staff to maintain MNCH/PMTCT clinic as expected (2-5 days per week)

The MRV-CCD and MR communities each have additional recruitment criteria.

MRV-CCD catchment communities should also:

- Be located in Nzega or Igunga districts
 - Exclusion: Malezi CCD-program supported facilities in Tabora Municipal, because there are no comparably urban facilities in non-Malezi districts.

MR facility catchment communities should also:

- Be located in Kaliua or Uyui
- Have new antenatal care attendees in the past year comparable to facilities in MRV-CCD communities (within about 25% variance).

Given the small cluster size, it was not possible to randomly allocate sites to intervention groups.

Sampling within Study Communities

Study communities are defined as the villages within the catchment area of the selected health facilities (n~30). The NBS EA census maps, estimating the total number of households in that EA as of the last census (2012) will constitute the sampling frame. The sampling unit will be the EA, and the sampling approach will use probability proportional to size (PPS). This will result in the final selection of EAs being statistically representative of the total population within selected study communities of each study district.

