EAs average about 50 households, and do not overlap with other recognized administrative units (ward, village, hamlet, street), but their area and population size could vary from 20-100 households, and household size varies as well. The most recent census showed 19% of rural households had children under 5 years, and that Tabora averaged six persons per household. Since this evaluation targets caregivers of children 0-24 months of age at the time of recruitment, that means that an estimated 7.6% of households would be considered eligible ($[19/5]*2$). Thus a sample of about 250-300 EAs will be selected, using the estimate of 8% of households being eligible. Then, recruitment rates will be monitored to know whether additional EAs will be needed or not. In case they are needed, a second sampling also using PPS will be done, and all households in the second-sample EAs will be visited. In case too many EAs are sampled, and our expected sample size would be far exceeded by including all sample EAs, targets by ward will be calculated (proportional to expected sample size), and once the target has been reached within a ward, no additional EAs will be included for that ward. However, once an EA is “opened,” all households in that EA should be enumerated, even if the target is then exceeded for that ward.

Recruitment into the Caregiver Cohort

Recruitment into the caregiver cohort will take place in two stages, whereby potentially eligible caregivers are identified through household enumeration, screened for study eligibility, and invited to verbally consent to participate in the listenership survey (stage I). On another day during the baseline data collection period, all eligible and participating caregivers will be revisited for re-screening, informed consent, enrolment into the caregiver cohort, and full baseline survey administration (stage II). We expect less than 5% loss between recruitment into in stage I

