Descriptive statistics (range, median, mean, percent) will be used to review the data overall and describe participant background characteristics, radio listenership patterns and parenting perceptions, knowledge and practices, identifying any baseline differences in population by study group. Confidence intervals (CI) will be calculated around summary measures and statistical tests of significance (non-parametric) will be applied where appropriate to compare the distribution of characteristics or outcomes across study groups. The effects of radio exposure only (objective 1) will be described by comparing study outcomes at baseline and endline within the MR study group only. Within study group differences in study outcomes will be described comparing distributions of responses to key outcome variables at baseline and endline using statistical testing appropriate for paired groups such as the paired t-test, Wilcoxon or McNemar's tests. Regression modelling may be used to estimate the intervention effect while controlling for covariates.

The additional effects of the combined exposure to radio, short videos and Malezi CCD (MRV-CCD; objective 2), as compared to the radio only effect, will be described using a differences in differences (DID) analysis. The treatment effect can be found by obtaining the proportion of caregivers with the outcome in the MRV-CCD and MR groups at both time periods. The difference in outcomes between study groups at both time periods may be charted to visualize the DID as shown in Figure 4, whereby the DID is what remains after subtracting the baseline differences between the two groups from the endline differences (30-5% = 25%). This will give an estimate of the extent of the improvement by the Malezi II full intervention. We will use regression modelling to estimate the intervention effect while controlling for covariates. We will use the following general form model:

$$Y = \beta_0 + \beta_1[\text{Intervention}] + \beta_2[\text{Time}] + \beta_3[\text{Intervention} \cdot \text{Time}] + \beta_4[\text{Covariates}] + \varepsilon$$

The interaction term coefficient β_3 will also estimate the extent of the DiD.

[figure not shown]

Figure 4. Differences in differences analysis graphic

Objective 3: Community Health Worker Cohort

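### The caregiver and CHW sample sizes carry a design effect (1.2 and 1.1), but every within-group test the protocol names assumes independent pairs; run unadjusted, the Objective 1 error could reach about 7.4% rather than 5%

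*Protocol*

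**What the plan says.** **Sizing.** Protocol, Sample Size Calculations, Objective 1, sets the caregiver sample "taking into account 15% LTFU, design effect of 1.2, and estimated correlation of 0.4 between respondents at baseline and endline". The footnotes to Tables 3 and 5 name the method as "STATA 14 paired proportions large-sample" McNemar's test at the 5% level. Objective 2 applies the same inflation ("Taking into account a 15% non-retention rate and a design effect of 1.2"). Objective 3 sizes the CHW cohort "taking into account a correlation of 0.4 between measures, a 5% non-retention rate and a design effect of 1.1".

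**Sampling.** Under Selection Criteria for Study Communities, "The health facilities will be purposefully selected". Under Sampling within Study Communities, "The sampling unit will be the EA", drawn with probability proportional to size, and "Thus a sample of about 250-300 EAs will be selected". CHWs are recruited through 12-16 full-intervention facilities.

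**Analysis.** Data Analysis, Objectives 1 and 2, says that within-group change will be assessed with "statistical testing appropriate for paired groups such as the paired t-test, Wilcoxon" or McNemar's test. Regression is optional there, and its stated purpose is covariate control. The difference-in-differences (DID) equation is a general form with one error term; it mentions neither clusters nor the link between a caregiver's two surveys. Objective 3 refers back to similar analyses and names no test. The protocol nowhere mentions cluster-robust errors, random effects, GEE or a survey-design adjustment.

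**The concern.** The sizing and the analysis rest on different variance assumptions. The sizing lists the within-person correlation (0.4), the loss to follow-up and the design effect separately, so the design effect is an extra variance allowance on top of the pairing. The named tests use the pairing, and so the 0.4, but they assume no dependence between one caregiver and another in the same EA, or between CHWs at the same facility.

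An analyst who follows the text would run a test whose standard error is too small by a factor of the square root of the design effect. That matters most for Objective 1, where the radio-only effect is judged by pre-post change within the radio-only (MR) group alone. It matters less for the CHW comparison in Objective 3. In both, the enrolled sample already pays for the clustering allowance, so leaving it out of the analysis gives up error control for no saving.

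**Working it through.** **1. Reproduce the plan's figures.** Inputs from Sample Size Calculations: 10% to 15%, correlation 0.4, 80% power, 5% level. Sidedness is not stated; two-sided reproduces the tables, while one-sided would give 330 in the first row of Table 3.

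- Discordant probability: pd = p1(1-p2) + p2(1-p1) - 2 x 0.4 x sqrt(p1 q1 p2 q2) = 0.085 + 0.135 - 0.8 x sqrt(0.09 x 0.1275) = 0.1343.
- n = [1.96 sqrt(pd) + 0.8416 sqrt(pd - 0.05^2)]^2 / 0.05^2 = 419.3, so 420 (as stated).
- Inflation: 420 x 1.2/0.85 = 592.9, so 593. For Table 4, 430 x 1.2/0.85 = 607.1, so 607.
- CHWs, 50% to 65%: pd = 0.3092, n = 105.5, so 106; 106 x 1.1/0.95 = 122.7, so 123.

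All agree with the tables, so the design effect was applied to a paired McNemar n.

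**2. Error when a design effect DE is ignored.** If the true variance of the change is DE times what the test assumes, the two-sided error is 2[1 - Phi(1.96/sqrt(DE))].

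| Clustering part of DE | 1.96/sqrt(DE) | True error | Coverage of a 95% interval |
|---|---|---|---|
| 1.05 (assumed) | 1.913 | 5.6% | 94.4% |
| 1.1 (CHWs, or assumed for caregivers) | 1.869 | 6.2% | 93.8% |
| 1.2 (caregivers, whole DE) | 1.789 | 7.4% | 92.6% |

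At 1.2 a chance change is declared significant 7.36/5 = 1.47 times as often as stated; at 1.1, 6.17/5 = 1.23 times.

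**3. Simulation check.** No true change, DE 1.2, 516 retained MR caregivers (607 x 0.85), 40,000 runs per setting. Assumptions: 10% prevalence, correlation 0.4, and the 250-300 EAs split evenly, giving 125-150 per arm. With EAs as clusters, unadjusted McNemar rejects in 7.3% to 7.4% of runs, and a cluster-robust test on the change in 5.0% to 5.1%. A separate simulation with about 504 completers (593 x 0.85) in 12-16 clusters gives 7.3% to 7.7% unadjusted, against 5.1% with no clustering.

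**4. Power after adjustment, Objective 1.** 516/1.2 = 430 effective pairs. The noncentrality is 0.05/sqrt(0.1318/430) = 2.856, where 0.1318 = 0.1343 - 0.0025. With t on 124-149 df, power is 80.9% to 81.0%. Interval width rises by sqrt(1.2) - 1 = 9.5%, or 10.4% to 10.6% with the t critical value.

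**The case against.** The strongest reply is that variance estimation is ordinary analysis-plan detail. The list of tests is introduced as examples, regression is allowed, the DID equation is only a general form, and no sentence says that pairs will be treated as independent. A plan that is not shown may name an adjusted test. This stands as a reason to keep the claim conditional. It does not remove the point: every example given fails in the same way, one of them is the test used for sizing, and the optional regression is tied to covariates. The protocol is therefore at odds with its own sizing basis, not merely silent.

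Second, the protocol does not say what the design effect covers. EA sizes range from 20 to 100 households, so part of the 1.2 may be allowance for unequal weights, which an unweighted paired test does not incur. Taking weighting as 1 + CV^2 of EA size, with an assumed mean of 50 and SD of 15-20, that part alone would be 1.09 to 1.16. This also stands. It makes 7.4% an upper figure at the plan's own design effect, with 5.6% to 6.2% if clustering contributes only 1.05 to 1.1.

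Third, Objective 3 names no test, and its outcome is a checklist score averaged over sessions, not a binary pair, so its 6.2% is doubly conditional. Fourth, Objective 1 is a descriptive, uncontrolled pre-post comparison without a single decision rule, so an excess of this size would seldom change its reading. Both are fair and limit the weight of the point.

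**Conclusion.** The mismatch is real and worth correcting, but modest. At the plan's own design effect, the two-sided Objective 1 error is up to about 7.4%, and up to about 6.2% for Objective 3. These figures require that the named tests (or, for CHWs, similar ones) are run unadjusted and that the whole design effect is clustering of the within-person change.

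Three stronger readings are tempting, and the document does not support them:

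- **That the Objective 1 error simply is 7.4%.** The tests are given as examples, and the composition of the 1.2 is not stated.
- **That Objective 1 must lose power to a small number of facilities.** Facilities are purposefully selected and the EA is the stated sampling unit, so the design does not require facility-level inference for caregivers. With the EA as cluster, power stays at about 81%.
- **That the DID for Objective 2 is anti-conservative in the same way.** If it were fitted with independent errors, its standard errors would probably be too wide, given a within-person correlation near 0.4. That correlation is an assumption here, since none is stated for the DID.

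The sample sizes themselves reproduce exactly and are not in question.

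**What to change.** - **Data Analysis, Objectives 1 and 2:** require the within-group pre-post comparisons to use a cluster-adjusted paired analysis, such as cluster-robust standard errors on each caregiver's change, GEE or a mixed model, with the EA as the cluster. Say what the design effects of 1.2 and 1.1 represent and at which level.
- **DID model:** link each caregiver's two surveys and use cluster-robust standard errors.
- **Objective 3:** cluster CHW changes by facility, with a small-sample correction for 12-16 facilities.

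The cost is wording and code, with no new data or participants. Objective 1 intervals widen by about 10%, which the planned sample already covers. Objective 3 intervals widen by sqrt(1.1) - 1 = 4.9% from the design effect, also already covered. The small-sample correction adds to that: with t critical values on 11-15 df, the total is sqrt(1.1) x 2.201/1.96 - 1 = 18% down to sqrt(1.1) x 2.131/1.96 - 1 = 14%. Some Objective 3 power is lost through the correction. A Wald approximation for a binary outcome goes from 82.2% to 74.7%-76.9%, but this is only indicative because the actual outcome is an averaged score.

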The Conrad N. Hilton Foundation supports EGPAF to implement a targeted early stimulation program at selected facilities in Tabora region to integrate extended ECD interventions into reproductive and child health (RCH) and HIV services for young children regardless of their HIV status. During the first phase (2016-17) of the Hilton-supported Malezi I Project (*caring for young children* in Kiswahili), EGPAF adapted and supported implementation of an early child development package into MNCH, PMTCT, and HIV care and treatment services at 47 EGPAF-supported facilities in three districts: Nzega, Igunga, and Tabora Municipal. The Malezi I intervention was adapted from the CCD curriculum in Tanzania by EGPAF in collaboration with Aga Khan Foundation, UNICEF and MOHCDGEC and translated into Kiswahili before being delivered to health care providers. The classroom and field based training was focused on building providers' counseling skills and understanding the concept of responsive caregiving. Specific topics included counseling caregivers on how to identify children's cues and respond to them appropriately; provide a safe and stimulating environment in the home; help caregivers understand if their children are developing well, recommend age appropriate play and communication activities, identify children with disabilities or developmental delays, provide and follow-up on referrals for specialized care as needed, and facilitate CCD group counseling. In addition to training, supervision and mentorship, the Malezi I program provided paper-based monitoring and evaluation (M&E) tools, and job aids from the CCD package to support group and home-based counseling, primarily done by CHWs, although health providers may also lead health education groups at the facility. The full Malezi I CCD intervention package included:

- ECD (CCD-based) knowledge and education/counseling skills training to facility-based and community health providers, including translated CCD-based manual with job aid
- Continuing supportive supervision to Malezi-supported facilities and CHWs
- M&E tools
- Toys (mostly home-made or safe household objects) and play mat for use in facility group sessions and during home visits
- Creative toy building training to support sustainable replenishment of toys for ECD sessions.

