The Malezi II *minimal intervention package*, composed of radio messaging only (**MR**), will reach all areas in Tabora, including those where the Malezi program has not been established. The Malezi II *full intervention package*, composed of radio messaging, the introduction of short video job aids primarily for CHW use, and the Malezi I CCD program (**MRV-CCD**), will be implemented in Malezi program districts, namely, Nzega, Igunga and Tabora Municipal.

The theory of change underlying the Malezi II full intervention package design draws on current evidence for CCD (6,20) and behavior change literature (41). It proposes that a combination of caregiver attitudes and norms (informed by access to information) will influence caregiver intentions to behavior, and ultimately their behaviors. Beyond providing caregivers with information to improve their knowledge, Malezi II supports caregiver capacity to make the desired changes to their caregiving behaviors through group learning (supported by video job aids) and practice and feedback (supported through home visiting).

While caregivers may develop an intention to change through program support, actual behavior change could be limited by a lack of skills (capacity) or not being in an appropriately enabling environment. We hypothesize that the addition of enhanced support from the CHW (short video job aids) and a more enabling environment from their family members and/or community (radio messaging) will lead to behavior change.

The theory of change is summarized in **Figure 1**.

[figure not shown]

Figure 1. Overview of theory of change

This conceptual model of behavior change underpins the hypothesis that the combined intervention of facility-based ECD resources and messaging from providers, CHW group and individual counseling in the home and facilities, with support from video job aids, and community-targeted mass media radio ECD messaging will have a stronger impact on caregiving behaviors, compared to radio messaging alone. It targets two potential pathways to caregiving behavior change: direct educational messaging to increase knowledge; and opportunities for practice and feedback to increase capacity. However, this augmented Malezi II program model is resource intense. Thus, the research design examines the relative benefits of additional resources to change caregiver behaviors, compared to the benefits of radio messaging alone, which is potentially more efficient and scalable.

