STUDY AIMS, OBJECTIVES AND RESEARCH QUESTIONS

Based upon the conceptual model described above, we have articulated research aims to derive specific and measureable objectives. These are presented below in terms of overall aims, specific objectives, and illustrative research questions, corresponding to each aim and objective.

Aims

1. Evaluate the effect of Malezi II radio (MR) messaging on caregiver awareness of children's developmental needs
2. Evaluate the extent to which the Malezi II full intervention (MRV-CCD: radio messaging, video job aids, continued CCD program support) increases caregiver knowledge and

practices as compared to a radio campaign alone (MR), using a quasi-experimental research design

- Evaluate the effect of Malezi II training and video job aids on the quality of community health care worker counseling support, provided in clinics and home

Objectives

- To determine caregiver radio listenership patterns at baseline, exposures to the ECD radio messaging nine months' post-intervention, and effect of radio exposure on caregiver ECD perceptions, knowledge and reported parenting practices, using pre-post structured interviews in a cohort of caregivers of children age 0-24 months at baseline, in study communities from each intervention arm.
- To determine whether the Malezi II full intervention (MRV-CCD) significantly increases caregiver's knowledge and parenting behaviors/practices when compared to radio messaging alone, using a pre-post quasi-experimental evaluation design with structured interviews, in a cohort of caregivers of children age 0-24 months at baseline, in MRV-CCD and MR communities.
- To determine whether the introduction of short video job aids (training, provision, supportive supervision) to the Malezi II CCD program improves the quality of counseling provided by the CHWs in the clinic and the home, using pre-post observation fidelity checklists for all CHWs working in the MRV-CCD communities.

Secondary Objectives

- Describe community health worker perspectives with regard to the salience and relevance of the program to their work, barriers and facilitators to implementing the Malezi II program and experiences with use of the short videos as a job aid.
- Describe caregiver perspectives on the support they receive from community health workers, the expected/perceived role of CHWs in their community, on the short videos, and on ECD services in the health facility.

Research Questions

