- To what extent does the Malezi II radio messaging reach caregivers of young children?
- To what extent are caregiver ECD perceptions, knowledge and reported parenting practices changed after introduction of Malezi II radio messaging to their communities?
- Is there a relationship between reported listenership and/or message recall (dose) and caregiver ECD perceptions, knowledge and reported parenting practices?
- To what extent does exposure to the Malezi II full intervention (MRV-CCD: radio messaging, video job aids, continued CCD program support) improve caregiver knowledge and parenting practices?
- Does exposure to the Malezi II full intervention (MRV-CCD) improve caregiver knowledge and parenting practices significantly more than exposure to radio messaging alone (MR)?
- To what extent do the CHWs adhere to the Malezi II training with regard to use of the video job aids, delivery of complete and accurate ECD messages, and general quality of counseling support?
- Do the Malezi II video job aids improve the quality of CHW ECD counseling support given to caregivers in clinic and home settings?

METHODOLOGY

This study is a two-arm quasi-experimental pre-post evaluation design, comparing two interventions to establish their relative impact on caregiver knowledge and behaviors/practices among a cohort of caregivers of children 0-24 months at enrolment (baseline) and under three years after a 9-month

intervention exposure period (endline). In addition, the quality of counseling support to caregivers, at health facilities and through home visits, will be assessed at baseline and endline in a cohort of CHWs recruited from the MRV-CCD full intervention group. Figure 2a provides an overview of the research design for objectives 1 and 2. Figure 2b provides an overview of the research design for objective 3.

[figure not shown]

Figure 2a. Research design overview – community component

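### The difference-in-differences is presented as the full package's effect over radio, but it estimates only the increment beyond radio in areas where CCD was already running at baseline

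*Protocol*

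**What the plan says.** Data Analysis (Objectives 1 and 2: Caregiver Cohort) uses the DID to describe "The additional effects of the combined exposure to radio, short videos and Malezi CCD (MRV-CCD; objective 2), as compared to the radio only effect". It defines the quantity: "the DID is what remains after subtracting the baseline differences between the two groups from the endline differences". It then says of the result: "This will give an estimate of the extent of the improvement by the Malezi II full intervention". The interaction coefficient β3 is said to estimate the same thing.

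On timing:

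- The background section on Malezi I places the first phase of CCD, in 2016-17, "at 47 EGPAF-supported facilities in three districts: Nzega, Igunga, and Tabora Municipal". The Location section draws the MRV-CCD arm from the first two of these districts.
- The Intervention Description says CCD in these areas dates from 2016 and has been supported without a break. Table 2 dates it 2016-17.
- Sample Size Calculations says the MR group has had no CCD exposure.
- The Intervention Description has two things starting after baseline: radio in both arms, and videos in MRV-CCD only.

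On the comparison wanted: the theory-of-change section counts the Malezi I CCD program as part of the full package and hypothesises that the combined intervention "will have a stronger impact on caregiving behaviors, compared to radio messaging alone". Aim 2 spells the package out as "radio messaging, video job aids, continued CCD program support". Objective 2 reads "To determine whether the Malezi II full intervention (MRV-CCD) significantly increases caregiver's knowledge and parenting behaviors/practices when compared to radio messaging alone", and neither it nor the comparative research question repeats that CCD is a continuing component.

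**The concern.** A DID can only credit the intervention with what changes after baseline. One of the three named components, CCD, was in place in one arm years before baseline. The Data Analysis section nevertheless gives the DID a meaning that includes CCD as a whole.

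The label decides how the result is read. The theory-of-change section says the design weighs a resource-intense model against radio alone, and the policy section says the findings will inform decision makers. Under the present label, a null DID would be read as showing that the full package is no better than radio. The DID cannot show that, because CCD effects present at baseline have been subtracted. A positive DID would be quoted as the package's effect, when it is a gain on top of established CCD. If CCD had already improved outcomes by baseline, and that gain persisted, the DID would understate the package's advantage over radio.

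**Working it through.** **1. What the DID contains.** Write, for one outcome:

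- m: MR level at baseline
- g: difference of the MRV-CCD districts from MR that is not due to CCD (either sign)
- c: CCD effect already present at baseline in MRV-CCD
- R: change in MR over the nine months (radio plus common trend)
- d: any difference in radio's effect where CCD exists
- v: effect of the video job aids
- k: effect of CCD contact accruing during the nine months

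| | Baseline | Endline |
|---|---|---|
| MR | m | m + R |
| MRV-CCD | m + g + c | m + g + c + R + d + v + k |

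Baseline gap = g + c. Endline gap = g + c + d + v + k. So DID = d + v + k, given parallel trends. The package's effect over radio, net of district differences and with the earlier CCD effect persisting, is c + d + v + k. The two differ by c, whatever its size.

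**2. The plan's own figures (Table 4).** MR goes from 10% to 15% and MRV-CCD from 25% to 45%.

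- Baseline gap: 25 − 10 = 15 points
- Endline gap: 45 − 15 = 30 points
- DID: 30 − 15 = 15 points, as stated; equivalently 20 − 5 = 15
- Share of the endline gap removed: 15/30 = 50%

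The illustration in Data Analysis uses other numbers: 30 − 5 = 25, so 5/30 = 17% is removed.

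**3. How much of the 15 points is CCD.** Only the sum g + c = 15 is given. Sample Size Calculations reports changes of 10-30 points in Malezi I when CCD was introduced. Values of c, which are assumptions for illustration, leave the DID untouched:

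| c (assumed) | g = 15 − c | DID | Package over radio = c + 15 |
|---|---|---|---|
| 0 | 15 | 15 | 15 |
| 10 | 5 | 15 | 25 |
| 15 | 0 | 15 | 30 |
| 30 | −15 | 15 | 45 |

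All four rows fit Table 4 equally well. A large simulation of the third row (radio +5, further increment +15) returned a DID of 15.1 points and an endline gap of 30.0.

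**4. CCD is not wholly removed.** Table 2 expects 2-4 clinic group sessions and 3-6 home counselling sessions in nine months. The section on observed sessions expects about 150 of 607 MRV-CCD index children (150/607 = 25%) to be under 6 months, so their caregivers have had little time for CCD contact about that child before baseline. This is the term k, and it stays in the DID.

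**5. Sample size.** 430 × 1.2/0.85 = 607 per arm, 1214 in total, as stated. Nothing above alters this.

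**The case against.** The strongest reply is that the protocol already says this. Aim 2, and the research question just before the comparative one, describe CCD as continuing. The Intervention Description says the MRV-CCD arm tests the addition of media and videos where CCD already exists. The Malezi II background section sets the within-arm pre-post change against CCD support without radio and video. A reader who carries those definitions forward will read the DID correctly. Baseline proportions will also be reported by group, so a gap would be visible.

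Much of this stands. It makes the problem an inconsistency centred on one section, not an undisclosed design feature. But Data Analysis is where the protocol says what the DID means. There the continuing qualifier is missing, while the theory-of-change section hypothesises about the whole package. A visible baseline gap does not tell a reader that the DID excludes whatever part of it CCD produced.

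A second reply is that Malezi II nearly doubles the number of supported facilities and admits CHWs trained under Malezi II or on the job, so some selected facilities may have had CCD only briefly. The documents do not settle this. Where it is so, c is smaller and k larger. The label is still wrong for the facilities that the Intervention Description describes as established.

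A reader might also infer that the trial is underpowered, since the only empirical basis given for the MRV-CCD change is the change seen when CCD was first introduced. The documents do not support that. Any smaller DID would be an assumption, and no stated sample size or power figure is shown to be wrong by this point.

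**Conclusion.** The concern holds as a matter of interpretation. Given CCD in place before baseline in one arm only, and given parallel trends, the DID estimates the increment beyond radio from video job aids, CCD contact accruing over nine months, and any difference in radio's effect where CCD exists. It is not the effect of the whole package over radio. The Data Analysis wording conflicts with the narrower readings in Aim 2, the Malezi II background and the Intervention Description.

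The planned gap that is subtracted is 15 of 30 points in Table 4 and 5 of 30 in the Data Analysis illustration. Two stronger readings should be resisted:

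- *That CCD accounts for those 15 points, or for at most 15.* Districts were not randomised and can differ in either direction, so the protocol neither gives nor bounds the CCD share.
- *That the DID isolates the videos.* Continuing CCD contact remains in it.

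The DID calculation and the regression model are not at fault. What needs correcting is the claim attached to them.

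**What to change.** In Data Analysis (Objectives 1 and 2), replace the description of the DID and of β3 with wording to this effect: the DID estimates the increment beyond radio from video job aids and continuing CCD, in areas where CCD was already established at baseline, assuming parallel trends; CCD effects present at baseline are excluded. Add two sentences: a null DID does not show that the full package equals radio alone, and a positive DID is not the full-package effect.

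In Objective 2 and the comparative research question, carry over Aim 2's qualifier ("radio messaging, video job aids, continued CCD program support") so that all three name the same comparison.

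The cost is a few sentences, best agreed before endline results are seen. No new data are needed, and the model, design and sample size do not change. The downside is a narrower headline claim for Objective 2.
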